The dose of 80mg once daily was selected for the extension cohort from a review of all available safety, tolerability, PK and efficacy data collected to date from this study At the IB data cut-off of 19 November 2013, AZD9291 had been administered across the dose range of 20 to 240mg once daily in this study: 20 mg (n=21), 40 mg (n=55), 80 mg (n=47), 160 mg (n=40) and 240 mg (n=7). No dose limiting toxicities (DLTs) have been reported at any dose level in the

escalation cohorts during the 21-day DLT evaluation period. Patients have once daily doses of AZD9291 for durations of up to at least 10 months depending on the dose level. Emerging efficacy data has demonstrated durable objective responses from the starting dose level of 20mg once daily (Ranson 2013). The selected 80 mg dose is four fold higher than the minimum efficacious dose tested in study D5160C0001, whilst still being one third of the maximum dose level investigated (240mg). The 80 mg dose level is considered to have a safety and tolerability profile appropriate for chronic administration to patients with advanced NSCLC.

The relative bioavailability of the tablet formulation of AZD9291 has been investigated in a healthy volunteer study (D5160C00005). Preliminary data from this study indicate that there is no clinically significant different in PK profile between a single 20mg dose of the current capsule formulation and a single 20mg dose of the tablet formulation (AZ data on file). Similarly, preliminary review of emerging PK data from a cohort of patients receiving once daily dosing with 80mg AZD9291 as the tablet formulation in this study indicates no clinically significant difference in the PK profile of the tablet formulation compared with the PK profile of the 80mg capsule formulation dosed to other patients in this study (AZ data on file).

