5.5 Study timetable and end of study

Planned duration of the study:

Study period:

Dose escalation, paired biopsy and expansion cohorts

The primary analysis of the expansions will take place 7.5 months after the last patient recruited starts investigational product or approximately 28 days after the final patient discontinues investigational product. The initial CSR will report the analysis of all primary and secondary endpoints and summarise the exploratory endpoints where data is available. During the primary analysis of the extension cohort an updated analysis of DoR from one or more of the expansion cohorts may be performed.

Extension cohort

The primary analysis of ORR will take place after all patients have completed at least two RECIST follow-up assessments (i.e. 3months). At this time, DoR and safety/tolerability will also be summarised. The primary analysis CSR will report the analysis of ORR supported by duration of response, and safety and tolerability data.

The full CSR will report the analysis of all primary and secondary endpoints (including updated ORR and DoR, DCR, PFS, OS, HRQoL and PK). This analysis will take place approximately 8 months after the last subject has been enrolled into the extension cohort, to allow responding patients to have a DoR greater than 6 months.

All cohorts

All patients will continue to be followed up for an updated analysis that will occur between 12-24 months after the last patient has been enrolled. All endpoints will be updated and summarised in an addendum to the CSR.

Any patients still receiving investigational product at the time of the final data cut-off will be able to continue to receive AZD9291 while deriving clinical benefit. Such patients will continue to be monitored for all Serious Adverse Events up to 28 days after the last dose of investigational product. Drug Accountability information must still be collected until all patients have completed treatment.

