7.9 Methods of statistical analysis

The statistical analyses will be performed by or other designated third party providers, under the direction of the

With the exception of some safety and PK summaries that may be combined, data from the dose escalation and the dose expansion cohorts will be presented separately. Data from the extension cohort will always be presented separately. Summaries from the extension cohort will be presented as a cohort and by previous treatment cohort (TKI only or TKI plus additional treatments).

The intent of all efficacy analyses from the expansion phase is that it be focussed on the population whose tumour T790M mutation status is identified via central testing. Patients central test results must match the cohort expansion group to which they were assigned (i.e. T790M+ in the 1st expansion). However, concordance between local and central testing of T790M status will be reviewed, and if deemed appropriate summaries incorporating local testing status may be produced. All summaries will present data by dose group.

Demographic data

Characteristics of the patients, including medical history and disease characteristics at baseline will be listed for each patient and summarised by dose group.

Reasons for discontinuation of investigational product will be listed including the study day of treatment discontinuation and will be summarised by dose group.

Exposure

Exposure to investigational product ie, total amount of study drug received will be listed for all patients.

Total exposure and total time on study (date of last dose minus date of first dose) will be summarised by the following: mean, standard deviation, minimum, maximum, median and number of observations. In addition, the number and percentage of patients with at least one dose interruption/dose delay and at least one dose reduction will be presented separately for the initial period defined as 21 days of multiple dosing (cycle 1) and for any time following this initial period of the study.

Safety

Safety data will not be formally analysed. All patients who receive at least one dose of AZD9291 will be included in the assessment of the safety profile (safety analysis set). At the end of the study, appropriate summaries of all safety data will be produced, as defined below.

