Data from all cycles of initial treatment will be combined in the presentation of safety data. AEs will be listed individually by patient and dose group. For patients who have a dose modification, all AEs (due to drug or otherwise) will be assigned to the initial dose group. The number of patients experiencing each AE will be summarised by the Medical Dictionary for Regulatory Activities (MedDRA) system organ class, MedDRA preferred term and CTCAE grade. The number and percentage of patients with adverse events in different categories (eg, causally related, CTCAE grade \geq 3 etc) will be summarised by dose group, and events in each category will be further summarised by MedDRA system organ class and preferred term, by dose group. SAEs will be summarised separately if a sufficient number occur.

Any AE occurring before the first dose of investigational product (ie, before study Day 1) will be included in the data listings but will not be included in the summary tables of adverse events.

Any AE occurring within the defined 28 day follow-up period after discontinuation of investigational product will be included in the AE summaries. Any adverse events in this period that occur after a patient has received further therapy for cancer (following discontinuation of investigational product) will be flagged in the data listings. AEs occurring after the 28 day follow-up period after discontinuation of investigational product will be listed separately, but not included in the summaries.

Haematology, clinical chemistry, vital signs, ECG data, ophthalmic examination data, demographic data and concomitant medications will be listed individually by patient and suitably summarised. For all laboratory variables, which are included in the current version of CTCAE, the CTCAE grade will be calculated. Summary statistics of mean, median, standard deviation, minimum, maximum and number of observations will be used.

Details of any deaths will be listed for all patients.

Any qualitative assessments will be summarised for all patients using the number of patients with results of negative, trace or positive.

Graphical presentations of safety data will be presented as is deemed appropriate. This may include, but is not restricted to, presentation of parameters against time, concentration or shift plots. Appropriate scatter plots will also be considered to investigate trends in parameters compared to baseline.

Pharmacokinetics

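### By-dose adverse event percentages pool all cycles without a common time window, so they partly reflect time on drug; a fixed-window table should stand beside them

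*Protocol*

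**What the plan says.** Under Safety, Section 7.9 of the protocol fixes the adverse event (AE) summaries as follows.

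- Cycles are pooled: "Data from all cycles of initial treatment will be combined in the presentation of safety data".
- The measure is a count and a crude percentage: "The number and percentage of patients with adverse events in different categories" is summarised by dose group, with examples such as causally related and grade 3 or higher.
- The counting period ends with each patient's own treatment: "Any AE occurring within the defined 28 day follow-up period after discontinuation of investigational product will be included in the AE summaries".
- Attribution stays with the starting dose: "For patients who have a dose modification, all AEs (due to drug or otherwise) will be assigned to the initial dose group".
- There is no formal comparison: "Safety data will not be formally analysed".

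The same section summarises total exposure and total time on study, and says "All summaries will present data by dose group". It splits dose interruptions and reductions into Cycle 1 and later, but does not split AEs.

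On observation time, Section 5.1.1 opens each dose only after review of the one before. Section 5.1.7 sets no maximum duration of treatment. Section 5.2 reports dosing "for durations of up to at least 10 months depending on the dose level" at the cut-off of 19 November 2013. Section 5.5 places the primary analysis of the expansions "7.5 months after the last patient recruited starts investigational product", or about 28 days after the final patient stops, with an update 12 to 24 months after the last enrolment.

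**The concern.** A percentage of patients with an event, counted for as long as each patient is on drug, rises with time on drug even when the underlying rate is constant. Two dose groups with the same rate but different observation times will show different percentages. If a higher dose was observed for less time, its toxicity is understated relative to a lower dose.

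Section 7.1 makes safety and tolerability the primary endpoint for escalation and expansion, and Section 7.2 ties it to recommending doses for future studies. Because no formal analysis is planned, the by-dose percentages are the main tabulated AE evidence on dose.

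The attribution rule adds to the problem. Section 5.1.1 lets patients who started below 80 mg be raised to at most 80 mg after at least 6 months and progression. Events after that increase still count against the lower starting dose.

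**Working it through.** The plan gives no figure to reproduce here, so the check asks how large the effect could be.

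**Inputs from the protocol**
- Steps from 20 to 240 mg at the doses listed in Section 5.2 (20, 40, 80, 160, 240): four.
- Minimum time per step: 7 days single-dose period (Section 3.1) + 21 days Cycle 1 + 2 days gap (Section 5.1.1) = 30 days. Four steps = 120 days, or 120/30.4375 = 3.9 months.
- Shortest potential follow-up at the expansion primary analysis, taking the first timing option in Section 5.5: 7.5 months.
- Longest treatment at 19 November 2013: at least 10 months. By then 21 + 55 + 47 + 40 + 7 = 170 patients had been dosed, of about 36 + 162 = 198 planned for escalation and expansion.

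**Follow-up contrasts**
- Minimum stagger: 7.5 + 3.9 = 11.4 months against 7.5.
- Extreme: if the last expansion patient starts after 19 November 2013, the earliest patients have at least 10 + 7.5 = 17.5 months against 7.5. This compares the earliest patient with the last, not group averages.

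**Assumptions (not in the protocol)**
Constant event rate h = 0.05 per month, and exponential discontinuation with a median of 9 months, so d = ln 2/9 = 0.0770 per month. The 28-day tail is ignored.

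**Formula**
Crude share with an event at potential follow-up c:
P(c) = h/(h+d) × (1 − exp(−(h+d)c)).

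**Equal rates (h = 0.05; h/(h+d) = 0.3937)**
- c = 7.5: 0.3937 × (1 − 0.3857) = 24.2%
- c = 11.4: 30.2% (using the unrounded 11.44 months)
- c = 17.5: 0.3937 × (1 − 0.1083) = 35.1%

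**Higher rate in the group followed 7.5 months, against 35.1% at 17.5 months**
- 1.5-fold (h = 0.075): 0.4934 × (1 − 0.3198) = 33.6%, so the excess is hidden.
- Double (h = 0.10): 0.5649 × (1 − 0.2651) = 41.5%, so it is visible but weakened.

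**Sensitivity to the assumed median, extreme contrast**

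| Median on drug (months) | 17.5 months, base rate | 7.5 months, base rate | 7.5 months, 1.5-fold | 7.5 months, double |
|---|---|---|---|---|
| 6 | 28.5% | 21.5% | 29.9% | 37.2% |
| 9 | 35.1% | 24.2% | 33.6% | 41.5% |
| 12 | 39.4% | 25.7% | 35.6% | 44.0% |

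**Update at 24 months, minimum stagger (27.9 against 24 months), median 9:** 38.2% against 37.5%.

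**Common window.** Four cycles are 84 days = 2.76 months, which every group completes well before 7.5 months of potential follow-up. With c = 2.76 for all groups, the same model gives 11.6% at the base rate in every group, 16.9% at 1.5-fold and 21.8% at double, whatever the order of opening. Cycle 1 alone (21 days) gives 3.3%, 4.9% and 6.5%.

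**The case against.** The strongest reply is that extra AE tables are ordinary content of a statistical analysis plan, which is not at hand, and that nothing in Section 7.9 forbids them. This stands in part: the absence of an exposure-adjusted table is not in itself a fault. But Section 7.9 does more than stay silent. It defines the by-dose AE summary as a pooled crude percentage, and that choice carries the bias.

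Other points stand more fully.
- Escalation is governed mainly by dose-limiting toxicity in a window that is the same for every dose (Section 5.1.3), and 80 mg was already chosen for the extension (Section 5.2).
- Time on study is summarised by dose group, so an imbalance would be seen. A separate exposure table does not, however, let a reader correct the percentages.
- Most patients at 20 to 160 mg exceed the 3 to 6 evaluable patients planned per escalation cohort. They come largely from expansions whose order of opening is not given, so the stagger between dose groups may be smaller or different.
- Line of therapy, T790M status and efficacy also affect time on drug and could lengthen it at any dose.

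A reader might infer that the percentages could reverse a dose-toxicity relation. If nobody ever stopped treatment, a 30% incidence at 17.5 months would correspond to 1 − 0.70^(7.5/17.5) = 14% at 7.5 months, and double the rate would read 26%, below 30%. The documents do not support that calculation, because AE counting ends 28 days after discontinuation. Keeping the 30% and allowing a median of 6 to 12 months on drug, the later group reads 19% to 23% at equal rates and 33% to 39% at double the rate. The doubling is not reversed. A reversal appears only at an early data cut: 10 against an assumed 3 months, with a median of 9 months, gives 23% at double the rate against 28%. That is not the planned primary analysis.

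A reader might also infer that late events are missed because visits become 6-weekly from Cycle 7. Section 6.4.3 asks about health problems since the previous visit, so the whole interval is covered.

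**Conclusion.** The point holds in a limited form. The by-dose AE percentages in Section 7.9 mix event rate with time on drug, and the protocol itself says that duration differed by dose level. Under the stated assumptions, equal rates would differ by about 6 percentage points at the expansion primary analysis with the minimum stagger (30% against 24%), and by about 11 points in the extreme contrast (35% against 24%). At that extreme a 1.5-fold excess in the later group would be roughly masked and a doubling weakened. By a 24-month update the difference is under 1 point.

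These figures rest on an assumed constant rate, an assumed discontinuation pattern and follow-up contrasts built from minimum timings or from the earliest and latest patients. It is not established that the higher doses are favoured, or that the dose comparison is driven mainly by exposure, because the protocol gives no duration per dose. The matter is moderate at most, but it touches a primary endpoint and is cheap to put right.

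**What to change.** Keep the all-cycles table. Add, by initial dose group, the number and percentage of patients with any AE, with an AE of grade 3 or higher, and with a causally related AE, within a common window from the first multiple dose: for example Cycle 1, and the first four cycles. State that by-dose AE comparisons are read from that table together with the exposure summary. Dose increases after at least 6 months cannot fall inside such a window, so they do not blur attribution there.

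Show exposure-adjusted first-event rates as supportive only. They assume a roughly constant rate, and they inflate groups with short exposure when events occur early. Section 3.2 expects the major toxicities within 21 days, so that case is likely.

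The cost is a few extra tables from data already collected, with no change in conduct. The common window leaves out late-onset events, and for escalation patients the single-dose period; both remain in the all-cycles table.

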The efficacy assessments of objective response (OR), duration of response (DoR), disease control rate (DCR), progression-free survival (PFS) as assessed by RECIST 1.1 and overall survival (OS) are widely accepted parameters for the assessment of efficacy for advanced NSCLC treated with EGFR TKIs (Sun et al 2010).

Preclinical data (Investigator Brochure Section 4.1.1.2) demonstrates that when the clinical efficacy in a dual mutation (L858R/T790M+) mouse xenograft model eventually develops resistance to low dose AZD9291 (1mg/kg/day) a dose escalation (to 25mg/kg/day) reverses the tumour regrowth and provides additional durable sustained tumour shrinkage. Therefore, an increase in dose of AZD9291 to a currently identified well tolerated dose (80 mg) in patients with initial objective responses but subsequent RECIST confirmed disease progression at a lower dose may have the potential to provide prolongation of the clinical benefit for these patients.

The collection of cerebrospinal fluid (CSF) will enable the investigation of the ability of AZD9291 to cross the blood brain barrier. Brain metastases occur in 20-30% of patients with advanced NSCLC, and are associated with poor prognosis (Porta 2011). The first generation EGFR TKI agents have demonstrated only limited efficacy in treating brain metastases (Bai 2013, Ranson 2013, Shimato 2006) however, preclinical data suggests that AZD9291 may be capable of crossing the blood brain barrier (Investigator Brochure) and potentially may offer better exposures in this anatomically protected location.

The collection of samples to allow investigation of the presence and/or identity of metabolites of AZD9291 and, if appropriate, characterise their pharmacokinetics will generate data to allow AstraZeneca to fulfil regulatory requirements related to the testing of the safety of metabolites.

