See Table 1 below for the proposed dose escalation scheme. All dose levels beyond cohort 1 may change in light of emerging safety and pharmacokinetic data. The planned dose escalations will not exceed doubling of the dose in principle. However up to a quadrupling of dosing may be permitted in the first two escalations only, if the drug concentrations from the first or second dose level are not measureable or are deemed to be far from predicted drug exposure (eg, greater than 2-fold difference) and there have been no significant safety or tolerability issues.

Cohort	Dose mg (to be administered once daily)	
1	20	
2	40	
3	80	
4	160	
5	200	
Х	XXX	

Proposed	dose	escalation	scheme
----------	------	------------	--------

There will be a minimum of 2 days between conduct of the last patient assessment required for SRC review from one cohort and the start of dosing in the subsequent cohort.

There will be no intra-patient dose escalations with the exception of patients who were started and have remained on treatment at a dose lower than 80mg for at least 6 months, have shown clinical benefit (as judged by the investigator) and have then developed RECIST confirmed disease progression. The escalated dose must be agreed in advance between the Investigator and AZ Study Physician, and will not exceed 80mg; which has been declared safe and tolerable by the SRC.

The dose for subsequent cohorts or a decision to stop recruitment to the escalation phase of the study will be agreed by the SRC after review of the data from each cohort (see Section 5.1.5).

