7. EVALUATION AND CALCULATION OF VARIABLES AND STATISTICAL METHODS

7.1 **Definition of study endpoints**

To meet the objectives for this study, data for the following endpoints will be collected:

- Safety and Tolerability (Primary for escalation and expansion)
- AZD9291 pharmacokinetics (and metabolites AZ5104 and AZ7550) (Secondary)
- Pharmacodynamics (Secondary)
- Tumour response including ORR (Primary for extension, secondary for escalation and expansion), DOR, DCR and PFS (Secondary)
- Overall survival (Secondary for extension only)
- Pharmacodynamic markers in EGFRm+ T790M+ tumours at selected clinical doses (Secondary)
- Patient Reported Outcomes (Exploratory)
- Metabolite identification (Exploratory)
- Other biomarker data (Exploratory)
- Pharmacogenetics (Exploratory)
- Diagnostic tumour samples (Exploratory)
- For the extension cohort only, an independent central review (ICR) of the RECIST assessments will be used for the primary analysis of ORR and other RECIST-based outcomes.

Safety endpoints are defined in Section 6.4. Derivations, calculations and analysis plans for each of these endpoints are presented below.

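### The initial-dose rule for adverse events has no exception for intra-patient escalation, so events arising after escalation are counted in the 20 mg and 40 mg columns

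*Protocol*

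**What the plan says.** The safety part of Protocol Section 7.9 fixes how AEs are assigned: "For patients who have a dose modification, all AEs (due to drug or otherwise) will be assigned to the initial dose group". The tables built on that assignment are by dose: "events in each category will be further summarised by MedDRA system organ class and preferred term, by dose group". Section 7.1 lists "Safety and Tolerability (Primary for escalation and expansion"), so these tables report a primary endpoint.

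Section 5.1.1 rules out raising a patient's dose, "with the exception of patients who were started and have remained on treatment at a dose lower than 80mg for at least 6 months". Such patients must also have shown clinical benefit and then had RECIST progression, and the sponsor's study physician must agree the new dose in advance. That dose "will not exceed 80mg; which has been declared safe and tolerable by the SRC". Section 3.2 gives the reasoning and describes "an increase in dose of AZD9291 to a currently identified well tolerated dose (80 mg").

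Section 5.2 gives the numbers treated at the 19 November 2013 cut-off: "20 mg (n=21), 40 mg (n=55), 80 mg (n=47), 160 mg (n=40) and 240 mg (n=7"). The only levels listed below 80 mg are 20 mg and 40 mg.

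**The concern.** Assigning AEs to the starting dose is a common convention when the dose can only go down. An event on a reduced dose then stays with the higher dose that the patient was first given. An upward change reverses this: an event that first appears on the raised dose is charged to a lower dose that the patient was no longer taking.

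At stake is the reading of the by-dose AE tables. The low-dose columns would mix events seen on 20 mg or 40 mg with events seen after escalation. The tables would also not show how patients tolerate being moved up, although these patients are the direct evidence on that question.

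**Working it through.** The plan gives no figure for this rule, so there is none to reproduce. The check is a comparison of the texts, followed by the size of the shift.

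**1. Does the rule reach escalated patients?** Section 7.9 speaks of any dose modification and of all AEs. It contains no exception for increases. Nothing else in the protocol asks for a summary by dose at onset, or for a cut-off or separate display after escalation. On its plain wording, the rule applies.

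**2. Which events move a table row?** The tables count patients by system organ class, preferred term and CTCAE grade. A repeat of an earlier term at the same or a lower grade adds nothing. A new term, or a higher grade of an earlier term, does.

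**3. Direction.** Compared with counting only events with onset on the initial dose, the rule can add patients to a low-dose row and cannot remove any.

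**4. Shift per patient**, with the Section 5.2 counts as denominators:
- 20 mg: 1/21 = 4.8 percentage points
- 40 mg: 1/55 = 1.8 percentage points

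Section 7.9 presents escalation and expansion data separately, apart from some summaries that may be combined. Where a column holds only part of the 21 or 55 patients, the shift per patient is larger. If a dose group has grown since the cut-off, it is smaller.

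**5. Illustration over a range.** Let p be the incidence at the initial dose, f the share of the dose group later escalated, and q the chance of a first onset after escalation in a patient without the event before. Then

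tabulated incidence = p + f × (1 − p) × q.

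The protocol gives none of p, f or q; all three are assumptions here.

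| f | p | q | Added to the row, f(1 − p)q |
|---|---|---|---|
| 5% | 20% | 10% | 0.05 × 0.80 × 0.10 = 0.4 points |
| 20% | 5% | 25% | 0.20 × 0.95 × 0.25 = 4.75 points (5% becomes 9.75%) |
| 30% | 5% | 25% | 0.30 × 0.95 × 0.25 = 7.1 points |

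The first and last rows are the extremes for f from 5% to 30%, p of 5% or 20%, and q of 10% or 25%.

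**6. What is not touched.** Under Section 5.1.3 the DLT window closes at the end of Cycle 1, whereas escalation needs at least 6 months on treatment. Escalated patients are never counted at 80 mg, so the column for patients who started there does not change. Section 7.9 always presents the extension cohort separately, and its 80 mg dose had already been chosen (Section 5.2).

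**The case against.** **The rule may not be meant to cover increases.** The same paragraph of Section 7.9 opens by pooling the cycles of what it calls initial treatment. Section 5.1.6.1 uses the term dose modifications for restarting at the same or a lower dose after toxicity, while Section 5.1.1 speaks of intra-patient escalation. But neither term is defined so as to leave escalation out, and the reference to all AEs reads against that. If the narrower meaning was intended, the protocol still does not say where AEs after escalation belong.

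**The consequence is limited.** This stands. Section 7.9 says that safety is not formally analysed, so only descriptive tables are affected. Eligibility for escalation is narrow and the number may be small. The listings and AE start dates would let a reader recover dose at onset with some effort. Some events after escalation would also have occurred had the dose stayed the same, so not every added count reflects the higher dose.

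**Stronger readings that the documents do not support.**
- A reader might see a contradiction with Section 7.8, which uses the dose actually received. That rule is for patients treated in error. Section 7.9 deals with patients treated as planned whose dose later changed, and both rules can operate together.
- A reader might infer that the AE rule also puts time on the raised dose into the low-dose groups. The rule concerns AEs only. The exposure part of Section 7.9 calls for summaries by dose group but does not say how an escalated patient's exposure is divided.
- A reader might conclude that the tolerability of 80 mg, or the choice of the extension dose, is distorted. The column for patients who started at 80 mg is unchanged and that choice had been made. Only the contrast with the lower doses is affected.

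**Conclusion.** The point holds as a fault in a stated rule. Applied as written, Section 7.9 counts new or higher-grade AEs after escalation under the starting dose. The low-dose rows can only rise, and the descriptive contrast with higher doses narrows wherever incidence increases with dose.

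The firm figures are the shifts per affected patient: about 4.8 points at 20 mg and 1.8 points at 40 mg, on the 19 November 2013 counts. The total effect cannot be fixed from the protocol, which gives no escalation rate. The range of 0.4 to 7.1 points per row rests wholly on the assumed values of p, f and q. The point is worth correcting because the tables report a primary endpoint, but it does not threaten dose-finding or the extension cohort.

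**What to change.** In Section 7.9, limit the initial-dose rule to dose reductions and interruptions. For patients escalated under Section 5.1.1:
- end attribution to the initial dose at the first escalated dose;
- summarise AEs with onset from that date, with the corresponding exposure, in a separate column;
- label that column *escalated* rather than *80 mg*, because Section 5.1.1 sets a ceiling and not a fixed dose;
- show dose at onset in the AE listings.

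The data are already collected: AE start dates under Section 6.4.3 and treatment details under Section 5.1.8. The programming is modest. The drawback is one extra column with few patients, selected for long treatment, benefit and then progression. It should carry a note that it is not comparable with the column for patients who started at 80 mg.
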